5.3. Adverse Event Severity

The investigator will use the following definitions to rate the severity of each adverse event:

Mild	Awareness of a sign or symptom that does not interfere with the subject's usual activity or is transient, resolved without treatment and with no sequelae
Moderate	Interferes with the subject's usual activity and/or requires symptomatic treatment
Severe	Symptom(s) causing severe discomfort and significant impact of the subject's usual activity and requires treatment

5.4. Relationship to Study Device

The investigator will use the following definitions to assess the relationship of the adverse event to the use of study device:

Not Related	Relationship to the device or procedures can be excluded when:
	The event has no temporal relationship with the use of the investigational device or the procedures related to the application of the investigational device.
	The serious adverse event does not follow a known response pattern and is biologically impossible.
	The discontinuation of medical device application or the reduction of the level or activation/exposure, when clinically feasible, and the re-introduction of its use do not impact on the serious adverse event.
	The event involves a body-site or an organ that cannot be affected by the device or procedure.
	• The serious adverse event can be attributed to another cause (e.g. an underlying or concurrent illness/clinical condition, an effect of another device/drug/treatment, or other risk factors).
	The event does not depend on a false result given by the investigational device used for diagnosis, when applicable.

Confidential Page 31 of 79

Possible	The relationship with the use of the investigational device or the relationship with procedures is weak but cannot be ruled out completely. Alternative causes are also possible (e.g. an underlying or concurrent illness/clinical condition, an effect of another device/drug/treatment). Cases where relatedness cannot be assessed, or no information has been obtained, should be also be classified as possible.
Probable	The relationship with the investigational device or the relationship with the procedures seems relevant and/or the event cannot be reasonably explained by another cause.
Highly Probable	The temporal sequence is relevant and the event abates upon device application completion/removal, or reappearance of the event on repeat device application (re-challenge).
	The serious adverse event is associated with the investigational device or with procedures beyond reasonable doubt when:
	The event is a known side effect of the product category the device belongs to or of similar devices and procedures.
	• The event has a temporal relationship with the investigational device use/application or procedures.
	• The event involves a body-site or organ that a) the investigational device or procedures are applied to or b) the investigational device or procedures have an effect on.
	 The serious adverse event follows a known response pattern to the medical device.
	The discontinuation of the medical device application (or reduction of the level of activation/exposure) and reintroduction of its use (or increase in the level of activation/exposure) impact on the serious adverse event (when clinically feasible).
	Other possible causes (e.g. an underlying or concurrent illness/critical condition or/and an effect of another device, drug or treatment) have been adequately ruled out
	Harm to the subject is due to error in use.
	 The event depends on a false result given by the investigational device used for diagnosis, when applicable.

Confidential Page 32 of 79

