2. DESCRIPTION OF THE STUDY DEVICE

The Chansu Vascular Technologies (CVT) Everolimus-coated PTA Catheter is an angioplasty

Confidential Page 13 of 79

¹ Trimukhe R, Vani P, Patel A, Salgotra V. Safety and performance of the EverProTM everolimus-eluting coronary stent system with biodegradable polymer in a real-world scenario. World J Cardiol. 2020;12(12):615-625. doi:10.4330/wjc.v12.i12.615

catheter designed to facilitate percutaneous treatment of subjects with documented symptomatic occlusion and/or >70% stenosis of the SFA or popliteal (P1 segment) artery.

The CVT Everolimus-coated PTA Catheter is comprised of two main components:

- 1) A CE-marked, commercially-available PTA balloon catheter (Ebony® 0.018" OTW PTA Balloon Catheter, Natec Medical Ltd. Reduit 72201, Mauritius) designed to treat peripheral vascular artery lesions. The PTA catheters are also previously cleared by FDA for peripheral (PTA) angioplasty indications (FDA classification LIT, K143041).
- 2) A drug coating comprised of an approved, commercially-available active pharmaceutical agent (API) mixed with an approved commercially-available excipient. The active pharmaceutical agent is the drug everolimus, in crystalline form, and it is applied onto the balloon using a glycerol ester excipient. Everolimus, like sirolimus, is an mTOR inhibitor drug with cytostatic properties. Everolimus is currently used in CE mark and FDA approved coronary drug-eluting stents [Promus (Boston Scientific), Xience (Abbott Vascular), Synergy (Boston Scientific)].

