5.2. Anticipated Adverse Events

An anticipated adverse event is any untoward medical occurrence in a subject which is predefined in the protocol and/or Instruction for Use (IFU) and that is identified or worsens during a clinical study, regardless whether or not the event is considered related to the study device or drug regimen prescribed as part of the protocol.

The following is a list of adverse events that may result from the PTA procedure.

- Abrupt closure
- Acute MI
- Allergic reaction to contrast, concomitant medications (Allergic Reaction)
- Amputation
- Aneurysm
- Arrhythmias (bradycardia & tachycardia)
- Arterial dissection
- Arterial perforation or rupture
- Artery spasm
- AV fistula
- Bleeding

Confidential Page 28 of 79

- Bypass graft surgery (emergent or non-emergent)
- Chest pain
- Death (cardiovascular or non-cardiovascular related)
- Discomfort during the procedure
- Embolism/PTA catheter embolism
- Endocarditis
- Fever
- Groin Bruising/Discomfort
- Hematoma
- Hemorrhage
- Hypertension
- Hypotension
- Injury to the groin blood vessel
- Infection or pain at insertion site
- Ischemia
- Nausea
- Pseudoaneurysm
- Renal failure
- Restenosis
- Sepsis /infection
- Stroke/CVA
- Wound complication or wound infection
- Thrombosis
- Total occlusion
- Vomiting / nausea

The oral formulation of everolimus has been evaluated in clinical trials and is approved worldwide for the prophylaxis of organ rejection in adult kidney transplant recipients at low-moderate immunologic risk and for the treatment of patients with advanced renal cell carcinoma. Oral dose of everolimus depending on the indication ranges between 1.5 and 20 mg/day. The following list includes the known risks of everolimus at these oral doses. The following is a list of theoretical adverse events that may result from the addition of everolimus to a PTA catheter:

- Abdominal pain
- Anemia
- Angioedema
- Anorexia
- Asthenia
- Constipation

Confidential Page 29 of 79

- Cough
- Delayed wound healing/fluid accumulation
- Diarrhea
- Dyslipidemia (including hyperlipidemia and hypercholesterolemia)
- Dyspnea
- Dysgeusia
- Dyspepsia
- Dysuria
- Dry skin
- Edema (peripheral)
- Epistaxis
- Fatigue
- Headache
- Hematuria
- Hyperglycemia
- Hyperlipidemia
- Hyperkalemia
- Hypertension
- Hypokalemia
- Hypomagnesemia
- Hypophosphatemia
- Increased serum creatinine
- Infections and serious infections: bacterial, viral, fungal, and protozoal infections
- Insomnia

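### Section 5.4 asks for one rating of relationship to the study device, but its grades can be met through the procedure alone, so the rating does not show which was responsible

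*Combined protocol and SAP*

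**What the plan says.** Section 5.4 of the protocol, titled for the study device, gives this instruction: "The investigator will use the following definitions to assess the relationship of the adverse event to the use of study device". One scale of four grades follows, and no second rating is requested.

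The grades bring in the procedure each time:

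- Not Related: "Relationship to the device or procedures can be excluded when".
- Possible: "The relationship with the use of the investigational device or the relationship with procedures is weak but cannot be ruled out completely".
- Probable: "The relationship with the investigational device or the relationship with the procedures seems relevant".
- Highly Probable: an opening definition that speaks only of the device, then a list introduced by "The serious adverse event is associated with the investigational device or with procedures beyond reasonable doubt when". One entry reads "The event is a known side effect of the product category the device belongs to or of similar devices and procedures".

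Other sections keep the sources apart. Section 5.2 has one list of events expected from the angioplasty procedure and another introduced by "The following is a list of theoretical adverse events that may result from the addition of everolimus to a PTA catheter". Section 2 describes the device as two components, the first being "A CE-marked, commercially-available PTA balloon catheter" and the second the drug coating.

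**The concern.** The heading and instruction promise an answer about the study device, but the grades answer a wider question: was the event linked to the device or to the procedure? Someone reading a tabulation of related events would take the rating at its label and would be misled wherever the link was procedural.

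This matters more here than in a randomised trial. The study is described as first-in-human (9.6) and is single-arm (3), so no uncoated-balloon group shows the background of procedural events. The sponsor also makes statements that depend on the distinction. Appendix J says its two high residual risks belong to the interventional procedure and are not specific to the coated balloon. Section 7.2 considers the side effects of high-dose everolimus unlikely at the dose on the catheter. A merged rating can neither support nor contradict either statement.

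**Working it through.** No arithmetic applies. The check reads 5.4 against the sections that feed it or use it.

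**1. Can a purely procedural event be graded as related?** Take an access-site haematoma that appears after the procedure and comes from arterial access.

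- Not Related is unavailable on its opening wording, because a relationship to the procedures cannot be excluded.
- Possible is met through its procedural half if the link is weak, and Probable through its procedural half if the link seems relevant.
- Highly Probable is undetermined. The entry on known side effects of similar procedures is met. The same list also contains a known response pattern to the device and the ruling out of other causes. The text does not say whether all entries or any one must hold.

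The event can therefore be recorded as Possible or higher on the scale headed for the study device.

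**2. Is the treatment of non-study devices clear?** Section 4.3 requires pre-dilatation of every target lesion with a non-study balloon. Section 3.2, in defining lesion and technical success, counts pre- and post-dilatation as part of the assigned device treatment, which points towards related. The Not Related criteria accept another device as an alternative cause, which points the other way. Two sites could grade the same pre-dilatation dissection differently, and the recorded grade would not show why.

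**3. Would an intraprocedural event be graded at all?** Section 5.1 starts adverse-event reporting once the index procedure is complete. Table 2 and Appendix F tick adverse events in the procedure column. These conflict. In addition, 3.7 counts a subject as enrolled only once the study catheter has entered the vasculature, and 4.3 makes a subject who needs a stent after pre-dilatation a screen failure. Some pre-dilatation events therefore fall outside the study.

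**4. Where is the rating used?**

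- Primary safety endpoint (3.1): a composite defined without causality.
- Secondary endpoints (3.2): none uses relatedness.
- Statistical analyses (6.4): no table by relatedness.
- Serious-event reporting (5.6(a)): triggered by a causal link to device or procedure, so a merged rating serves it.

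**5. Can event type do the separating?** In part. Access-site complications, arterial thrombosis and ipsilateral embolic events are separate secondary endpoints defined by event type. Appendix B classes deaths within 30 days as procedure related unless shown otherwise. The two lists in 5.2 help as well, but they overlap: hypertension, nausea, vomiting, infection and fever (pyrexia) stand on both, so the event term alone cannot assign those.

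**The case against.** The strongest reply is that little depends on this rating. No endpoint or planned analysis uses it, expedited reporting already combines the two sources, and the events most likely to be procedural are counted by type elsewhere. The wording of Possible and Probable names the two relationships in turn, so an investigator could apply the scale to each. The case report form (Appendix L) is only referenced and may already hold separate fields. One Not Related criterion also speaks of procedures related to applying the investigational device, so the term need not cover every step in the catheter laboratory.

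Most of this stands as a limit on the consequences. It does not remove the mismatch: the protocol asks for one rating, labels it for the device, and defines it so that the procedure suffices.

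A reader might infer three stronger things that the documents do not support:

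- **That procedural events will be graded Highly Probable.** The opening definition of that grade and two entries in its list point against this, and the combining rule is not stated.
- **That harm from the coating cannot be separated at all.** Event terms, the lists in 5.2 and the event-type endpoints allow partial separation. Conversely, splitting only device from procedure would leave coating and balloon merged.
- **That a main safety result is compromised.** A device-related event rate is not a planned output anywhere in 3.1, 3.2 or 6.4.

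**Conclusion.** The point holds in a limited form. As written, 5.4 allows an event caused only by the procedure to be recorded as related (Possible or higher) to the study device, and the rating by itself does not identify the source. The primary safety endpoint, the sample size and 5.6(a) reporting are unaffected. What suffers is the interpretation of the causality rating and of any relatedness table drawn from it.

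The number of subjects affected cannot be stated. The documents give no rate of access-site or pre-dilatation events, and the start of adverse-event recording is itself contradictory. The conclusion assumes that the form follows the protocol text. If it already has separate fields, only the protocol wording and the tables need to change. This is a cheap improvement worth making, not a flaw that invalidates the safety assessment.

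**What to change.** 1. In 5.4, and on the adverse-event form if it does not already do so, rate each event separately on the same scale for (a) the procedure, meaning access, pre-dilatation, contrast and non-study devices; (b) the study balloon catheter; and (c) the everolimus coating. State that (c) rests on judgement, since there is no uncoated control.
2. State for each grade whether its criteria are all-of or any-of.
3. Add to 6.4 adverse-event tables by each attribution.
4. Keep 5.6(a) reporting as broad as it is now by letting any of the three ratings trigger it.
5. Reconcile 5.1 with Table 2 and Appendix F on whether events during the procedure are recorded and graded.

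The cost is one or two extra fields on the form, back-completion for events already recorded, and a few descriptive tables. Endpoints, sample size and visit schedule do not change.

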5.5. Serious Adverse Events

An Adverse Event is considered serious if the event led to one of the following outcomes:

- Death of a subject
- Serious deterioration in the health of a subject that resulted in any of the following:
 - Life-threatening illness or injury
 - o Permanent impairment of a body structure or body function
 - o Hospitalization or prolongation of patient hospitalization
 - Medical or surgical intervention to prevent life-threatening illness or injury or permanent impairment to a body structure or body function
 - o Chronic disease
- Foetal distress, foetal death or a congenital physical or mental impairment or birth defect

Planned hospitalizations for pre-existing conditions or a procedure required by this protocol without serious deterioration in health is not considered a serious adverse event.

5.6. Procedures for Reporting Serious Adverse Event

Criteria for Reporting Serious Adverse Event

Serious adverse events are required to be reported for the following situations:

- a. Any serious adverse event that has a causal relationship with the investigational device or the investigation procedure or where such as causal relationship is reasonably possible.
- b. Any device deficiency that might have led to a serious adverse event if appropriate action had not been taken, intervention had not occurred or circumstances had been less fortunate.
- c. Any new findings in relation to any event referred to in points (a) and (b) above.

Reporting by the Sponsor to National Competent Authorities

The Sponsor must report serious adverse events to the National Competent Authorities (NCAs) where the clinical investigation has commenced per the following timelines:

- For all reportable events which indicate an imminent risk of death, serious injury or serious illness and that requires prompt remedial action for other subjects, users or other persons or a new finding to the event: *Immediately but not later than two (2) calendar days after awareness by the Sponsor of a new reportable event or of new information in relation with an already reported event.*
- For other reportable events or a new finding/update: *Immediately but not later* than seven (7) calendar days following the date of awareness by the sponsor of

Confidential Page 33 of 79

the new reportable event or of new information in relation with an already report event.

Reporting by the Clinical Trial Investigator to the Sponsor

The Clinical Trial Investigator will report to the Sponsor immediately but no later than three (3) calendar days after investigational site study personnel become aware of the event.

Risk Assessment

In conjunction with the Coordinating Clinical Investigator and/or, if need be, the Clinical Event Committee (section 10.4), the Sponsor shall decide whether, as a result of a serious adverse event, the safety of study participants is at risk or whether continuation of the trial is in jeopardy.

Corrective Measures

If any situation potentially jeopardizing the safety of subjects, users or third persons arise during a clinical trial or approved performance evaluation, the Sponsor and those persons carrying out the clinical trial or the performance evaluation shall immediately take all of the essential safety measures in order to protect subjects, users or third persons from direct or indirect danger. The Sponsor or his representative shall immediately inform the competent Authority and arrange for the competent Ethics Committee to be informed of the latest developments.

6. STATISTICAL DESIGN AND ANALYSIS

6.1. Statistical Overview of the Trial

The primary sample size calculation is based on the hypotheses that the primary safety and effectiveness endpoints meet pre-determined Objective Performance Criteria (OPC).

The OPCs for the primary safety and effectiveness endpoints have been determined using historical control data from published studies. Since this is a feasibility trial, the attainment of statistical significance is neither a necessary nor a sufficient condition for determining whether the device merits further study. For example, if the data exhibits a trend ($p \le 0.15$) toward statistical significance when compared to historical control and raises no safety concerns, it may be deemed worthy of further investigation. In addition, there will be a focus on estimating the magnitude of observed rates at 180 days post-procedure and the associated 95% confidence intervals.

6.2. Analysis Populations

The primary endpoints will be analyzed on the entire safety population and on the evaluable subject population, as appropriate.

The safety population will consist of all subjects who enrolled into the study and for whom the procedure had been initiated.

All effectiveness endpoints will be analyzed using the evaluable population, which consists of subjects who had no bailout procedure and at least one valid follow-up visit.

Confidential Page 34 of 79

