В	0159	15-Mar-2022	Added walking test or treadmill test to baseline functional status to assess walking distance (section 4.1); added completion of walking test or treadmill test to 6 month and 12 month follow up (section 4.6); added walking test or treadmill test to Table 2 schedule of events. Updated planned enrollment schedule in protocol summary section.		
С	0162	24-Mar-2022	Added stent post-dilatation clarification to use CVT device to section 4.3 "Criteria for Bail-Out Stenting".		
D	0168	28-Apr-2022	Revise Appendix M (angiographic core lab guideline) to include complete distal runoff images		
E	0189	02-Aug-2022	Corrected Appendix F (Schedule of Events) to include Walking/Treadmill Test at 6M/12M follow up. This change reflects the requirements in the body of the protocol and the Schedule of Events in Table 2.		

Confidential Page 6 of 79

PROTOCOL SUMMARY

Investigational Device	CVT Everolimus-coated Percutaneous Transluminal Angioplasty (PTA) Catheter (CVT EVE-PTA Catheter)			
Study Objective	To assess the safety and inhibition of restenosis of the CVT Everolimus-coated PTA Catheter in the treatment of subjects with de-novo occluded/stenotic or re-occluded/restenotic lesions in superficial femoral or popliteal arteries.			
Study Design	Prospective, multi-center, open, single arm study			
Number of Subjects	A total of 75 subjects will be enrolled			
Number of Sites	Up to eight (8) sites in Europe			
Primary Safety Endpoint	Freedom of Major Adverse Event (MAE) rate at 6 months post-procedure, defined as a composite rate of cardiovascular death, index limb amputation and ischemia-driven target lesion revascularization (TLR).			
Primary Effectiveness Endpoint	Patency at 6 months post procedure, defined as freedom from restenosis as determined by duplex ultrasonography (DUS) (peak systolic velocity ratio (PSVR) ≤2.4 or ≤50% stenosis) and freedom from ischemia-driven target lesion revascularization (TLR).			
Secondary Safety Endpoints	• Rate of Major Adverse Event (MAE) rate in hospital and at 30 days, 1-, 2- and 3-years post-procedure, defined as a composite rate of cardiovascular death, index limb amputation and ischemia-driven Target Lesion Revascularization (TLR).			
	 Rate of occurrence of arterial thrombosis of the treated segment. Rate of ipsilateral embolic events of the study limb. Rate of clinically-driven target lesion revascularization at 6, 12, 24 and 36 months. 			

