6.4. Statistical Analyses

Detailed analyses of the primary endpoints will be performed when all of the subjects complete their primary follow-up visit at 180 days. No effort will be made to impute or extrapolate data to replace missing values. All calculations will be based on available data with missing data excluded. Any unused or spurious data will be noted as

Confidential Page 36 of 79

appropriate in the final report.

Analysis of Primary Endpoints

The primary effectiveness endpoint of patency at six (6) months will be analyzed on a per-subject basis for the evaluable populations.

The primary safety endpoint of freedom from MAE at 6 months will be analyzed using the safety population.

For both primary endpoints (ffMAE and patency at 6 months), percentages and exact 95% confidence intervals using Clopper-Pearson's method will be calculated.

Analysis of Secondary Endpoints

All secondary endpoints will be analyzed for the per-treatment evaluable population descriptive statistics will be provided to gain better understanding of the data.

For binary variables such as MAE or technical success counts, percentages, and exact 95% confidence intervals using Clopper-Pearson's method will be calculated. For continuous variables, means, standard deviations, and 95% confidence intervals for the mean using the Gaussian approximation will be calculated. If the assumption of normality seems untenable, nonparametric summary statistics will be presented instead.

For time-to-event variables, such as time to target lesion revascularization, survival curves will be constructed using Kaplan-Meier estimates, and log rank test results will be displayed for descriptive purposes only.

Analysis of Other Data

The clinical laboratory values collected will be analyzed by tabulating the number and percentage of subjects with clinically significant changes from baseline for each parameter at each time point.

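### Section 6.4 puts every secondary endpoint, safety included, on an undefined evaluable set; the only such set defined leaves out treated bail-out subjects

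*Combined protocol and SAP*

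**What the plan says.** Section 6.2 defines two sets. The safety population is everyone enrolled in whom the procedure was started. The evaluable population "consists of subjects who had no bailout procedure and at least one valid follow-up visit", and its stated use is that "All effectiveness endpoints will be analyzed using the evaluable population". Section 6.2 mentions the safety population only in connection with the primary endpoints. It names no set for secondary safety endpoints.

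Section 6.4 is clear for the primary endpoint: "The primary safety endpoint of freedom from MAE at 6 months will be analyzed using the safety population". For the rest it says "All secondary endpoints will be analyzed for the per-treatment evaluable population", and under the same heading it gives MAE as an example: "For binary variables such as MAE or technical success counts, percentages, and exact 95% confidence intervals". Neither the per-treatment evaluable population nor a valid follow-up visit is defined anywhere.

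The endpoints concerned appear in the Protocol Summary, under the heading "Secondary Safety Endpoints", and in section 3.2. They include "Rate of Major Adverse Event (MAE) rate in hospital and at 30 days, 1-, 2- and 3-years post-procedure", thrombosis of the treated segment, ipsilateral embolic events, clinically driven TLR, access-site complications, and lesion, technical, clinical and procedural success.

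**The concern.** A safety rate should count everyone exposed to the device. Here the set is defined partly by what happened after exposure: whether the subject needed a bail-out, and whether the subject reached a visit. Bail-out subjects had a flow-limiting dissection or a residual stenosis that dilatation did not resolve, so they are subjects whose later course a reader of a first-in-human study (section 9.6) would want to see. Requiring a visit can also remove the subjects with the worst early outcome. For acute success, the exclusion may remove the very procedures the endpoint is meant to score.

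At stake are the secondary rates listed above. Section 6.1 treats the absence of safety concerns as part of its example of when the device merits further study, so these rates can bear on that judgement although they are descriptive.

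**Working it through.** **1. Is bail-out a post-treatment exclusion?** Under section 3.7, enrolment is complete once the study catheter is in the vasculature. Under section 4.3, a lesion that needs a stent after pre-dilatation is a screen failure. Bail-out stenting comes later, after the study balloon and an unsuccessful post-dilatation. A bail-out subject is therefore enrolled, treated and in the safety population, but outside the evaluable set.

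**2. Which MAE rates include these subjects?**

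| MAE time point | Set under 6.4 | Bail-out subjects counted |
|---|---|---|
| In hospital, 30 days | evaluable | no |
| 6 months (primary) | safety | yes |
| 1, 2, 3 years | evaluable | no |

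Events up to 6 months still reach the primary rate. After 6 months, section 6.4 plans no MAE rate for all enrolled subjects. The Kaplan-Meier curves stand under the same secondary heading and so use the same set.

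**3. What does the visit condition remove?** Section 4.6 starts follow-up after discharge, and pre-discharge assessments are a separate section (4.5). On that reading, a subject who dies in hospital has no follow-up visit and is not evaluable. The 30-day contact may be a telephone call. If a call is not a visit, a subject who dies before the 6-month visit is lost as well. The duplex worksheet in Appendix I lists pre-discharge as a visit; if that counts, only deaths before that scan are lost. Bail-out subjects are out on every reading.

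**4. The plan's own figures.** The 95% limits are Clopper-Pearson: lower = Beta⁻¹(0.025; x, n−x+1), upper = Beta⁻¹(0.975; x+1, n−x). For 11 MAEs in 75 (section 6.3), x=64 and n=75 give 75.3% to 92.4%, as stated. The evaluable count reproduces as 75×0.90=67.5, about 68. It allows for dropout alone, so no bail-out rate can be read from it.

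**5. One in-hospital cardiovascular death.**
- Safety population: 1/75=1.3% (0.03-7.2).
- Evaluable set, post-discharge reading: 0/74=0% (0-4.9).
- If that subject is one of 4 assumed bail-outs, either reading: 0/71=0% (0-5.1).

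**6. Direction of the effect on MAE.** Take the plan's 11/75=14.7% as a stand-in for a secondary MAE count. Assume b bail-outs, MAE risk in bail-outs r times that of others, and d further MAE deaths before any valid visit. MAEs among bail-outs are r×b×11/(75−b+r×b), rounded. The evaluable rate is (11 − bail-out MAEs − d)/(75−b−d).
- b=4, r=1, d=0: 0.59, rounded to 1; 10/71=14.1%.
- b=15, r=1, d=0: 2.20, rounded to 2; 9/60=15.0%.
- b=8, r=2, d=1: 2.12, rounded to 2; 8/66=12.1%.
- b=15, r=3, d=2: 4.71, rounded to 5; 4/58=6.9%.

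Equal risk and no early deaths leave the rate almost unchanged. Higher risk in bail-outs, or early deaths, lowers it.

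**7. Technical success.** Four bail-outs are assumed. Rates are per subject for simplicity, although the endpoint is labelled per device.

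| Bail-outs scored as | Other failures | Evaluable set | Safety population |
|---|---|---|---|
| all failures | 0 | 71/71=100% (94.9-100) | 71/75=94.7% (86.9-98.5) |
| 2 failures, 2 successes | 0 | 71/71=100% | 73/75=97.3% (90.7-99.7) |
| all successes | 0 | 71/71=100% | 75/75=100% |
| all successes | 2 | 69/71=97.2% | 73/75=97.3% |

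The plan does not settle which row applies. Section 3.2 scores the final residual stenosis and counts post-dilatation as part of device treatment, and section 4.3 says that stent post-dilatation, if performed, should use the study catheter. A stented subject might therefore be scored either way.

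**The case against.** The strongest points on the other side are these.

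- A reader might infer that 6.4 contradicts 6.2. It does not do so literally. Section 6.2 gives the evaluable set to effectiveness endpoints without saying that only they may use it, and it is silent on secondary safety endpoints. If acute success counts as effectiveness, the two sections agree, and the problem there is selection. The summary's safety heading is weak evidence, because the list below it also holds patency, ABI and the walking questionnaire. All of this stands. What remains is a mismatch with the evident purpose of the two populations.
- Early events are not hidden. The primary rate counts MAEs to 6 months in all treated subjects, the Clinical Events Committee rules on all deaths (section 10.4), and the stopping rule in section 3.9 is not limited to evaluable subjects. This stands, and it confines the gap to the secondary rates.
- Mandatory pre-dilatation, with screen failure when a stent is needed, should keep bail-outs few. This stands too. The counts of 4, 8 and 15 above are assumptions with no source in the documents.
- The secondary analyses are descriptive, in a feasibility study focused on 180-day rates. That lowers the urgency, but it gives no reason to leave treated subjects out of a reported safety rate.

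**Conclusion.** The concern holds as a defect of analysis set. Followed as written, section 6.4 removes enrolled and treated bail-out subjects from every secondary safety rate. If a follow-up visit means one after discharge, it also removes in-hospital cardiovascular deaths from secondary MAE. The uncovered gap is the in-hospital, 30-day and 1-, 2- and 3-year MAE rates and the other secondary safety rates, with no all-enrolled MAE rate after 6 months.

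The size cannot be fixed, because no bail-out rate is given. The illustrations run from no change to 1.3% becoming 0% for a single in-hospital death, and from no material change to 94.7% becoming 100% for technical success with 4 assumed bail-outs.

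Three stronger readings are not supported. The primary safety result is not compromised. The secondary rates are not certain to look better, since equal risk in bail-outs leaves MAE at 14.1% to 15.0% against 14.7%. Nor can a bias in 6-month patency be claimed: the documents do not say how the studies behind the performance criteria treated bail-outs, so its direction is unknown. This should be fixed, but it does not undermine the primary analysis.

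**What to change.** In sections 6.2 and 6.4:

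1. Assign all secondary safety endpoints (MAE at every time point, thrombosis, embolic events, TLR, access-site complications) and lesion, technical, clinical and procedural success to the safety population.
2. State how a subject who receives a stent is scored for technical success.
3. Define or delete the terms per-treatment evaluable and valid follow-up visit.

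The evaluable-set figures may be shown beside these. They still describe the balloon without a stent.

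The cost is wording and one extra table. No new data are needed: Table 2 schedules adverse events at every contact, the duplex worksheet records bail-out stenting, and the angiographic guideline asks for images of bail-out treatment. The downside is that reported rates may be slightly less favourable. The change settles who belongs in the analysis. It does not settle missing late follow-up, to which the rule that "No effort will be made to impute or extrapolate data to replace missing values" would still apply.
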